13.7.3 Analysis of intestinal microbiome

Microbial DNA is extracted using the Mag-Bind Universal Pathogen DNA Kit (Omega Bio-Tek). Briefly, 250 mg of the specimen is transferred to a deep-well plate for bead beating followed by DNA precipitation and purification following the manufacturer's instructions. Finally, DNA is eluted in 100 uls of Elution Buffer and stored at -80°C until further use. 16S sequencing libraries are generated by amplifying the v3-v4 hypervariable regions of the 16S gene in a polymerase chain reaction using primers F341 and R785. Resulting amplicons are tagged with unique molecular barcodes that are later used to demultiplex sequencing reads into individual sample buckets. Libraries are loaded on a MiSeq flow cell and sequenced following Illumina's loading instructions. Sequence data are retrieved from the instrument by converting base call format files into fastq files for data processing purposes.

MicrobiomeDX uses BacPro™, a proprietary algorithm, to inspect and validate sequencing files by employing demultiplexing, trimming, merging, and quality filtering steps. Paired sequencing reads are merged using an overlap of 25 bp allowing for 10 base mismatches. Merged sequences are dereplicated and clustered in a de-novo fashion using VSEARCH, while filtering out sequence chimeras and singletons. Representative sequences from each cluster are mapped against the SILVA database at 99% sequence identity to obtain accurate taxonomic classifications and relative abundances. In parallel, feature tables are constructed to derive alpha diversity indices, and distance matrices are built to derive beta diversity indices. The BacPro™ pipeline generates a comprehensive report that includes alpha diversity scores describing community richness and evenness, taxonomic composition with relative abundances, and beta diversity metrics to determine the in-between sample differences based on the bacterial communities identified.

13.7.4 Patient Reported Outcomes

Summary statistics of the scores for the derived functional and symptom quality of life scales according to the scoring manuals and global health status scores will be summarized and compared by treatment arm at each time point.

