- 1.4.2 To explore blood biomarkers of antitumoral immune activity as predictors of response or resistance to sacituzumab govitecan plus pembrolizumab compared to sacituzumab govitecan alone in patients with HR+ / HER2- MBC.
- To characterize serial changes in immune marker profile in peripheral blood mononuclear cells (PBMCs) and in plasma over the course of study treatment.
 - To explore whether induction of changes in the immunosuppressive and/or immune-stimulating marker profile in PBMCs correlates with disease response to therapy (PFS, ORR by RECIST 1.1, OS).
 - To investigate whether there is an immune marker (i.e., PD-L1) in circulating PBMCs that correlates to tumor infiltrating lymphocyte (TIL) percentage in baseline tumor.
 - To characterize serial changes of neoantigen burden in circulating tumor DNA and correlate with disease response to treatment (PFS, ORR by RECIST 1.1, OS).
 - To explore serial changes in blood biomarkers as mechanisms of resistance to sacituzumab govitecan plus pembrolizumab compared to sacituzumab govitecan alone.

- 1.4.3 To explore the structure and function of the gut microbiome as predictors of response or resistance to sacituzumab govitecan plus pembrolizumab compared to sacituzumab govitecan alone in patients with HR+ / HER2- MBC.
- To characterize structure and function of the gut microbiome at baseline and correlate with disease response to treatment (PFS, ORR by RECIST 1.1, OS).
 - To explore whether changes in the overall diversity of gut microbiome, estimated by Shannon index, correlate with disease response to treatment (PFS, ORR by RECIST 1.1, OS).
 - To explore correlates of resistance to sacituzumab govitecan plus pembrolizumab compared to sacituzumab govitecan alone in paired samples from baseline and at time of progression.
- 1.4.4 To explore patient reported outcomes as measured by the following:
- To assess and compare the impact of treatment on Health-Related Quality of Life (HRQoL) between treatment arms, using European Organization for the Research and Treatment of Cancer (EORTC) quality of life (QOL) questionnaire version 30 (QLQ-C30) and the European Quality of Life (EuroQOL) EQ-5D-5L instruments.

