9.9 Patient Reported Outcomes

We plan to assess patient reported outcomes utilizing the EORTC QLQ-C30 (Appendix E) and EuroQOL EQ5D-5L (Appendix F) instruments, as well as specific questions from the NCI PRO-CTCAE (Appendix G) library. The questions have been selected carefully to capture the most common adverse events associated with sacituzumab govitecan and pembrolizumab.

The QLQ-C30 measure comprises 9 multiple-item scales and 6 single items. Multiple-item scales of QLQ-C30 consisted of 6 functional scales (physical, role, emotional, cognitive, social and global QOL) and 3 symptom scales (fatigue, nausea and vomiting, pain). Six single-item scales of QLQ-C30 involve dyspnea, sleep disturbance, appetite loss, constipation, diarrhea and financial impact. All of the derived scales range in score from 0 to 100. For the overall HRQoL and functioning scales, a higher score is correlated with better HRQoL, whereas a higher score represents worse HRQoL for symptom scales.

The EQ-5D-5L generic QOL questionnaire is comprised of 5 dimensions: mobility, self-care, usual activities, pain or discomfort, and anxiety or depression. Each dimension has 3 levels: (1) no problem, (2) some problem, or (3) extreme problem. Thus, the final scoring consists of 243 possible combinations or health states. The utility value for each state is assigned on the basis of a set of preference weights (tariffs) elicited from the general population and is specific for each country.

PRO-CTCAE is a PRO measure developed to evaluate symptomatic toxicity in patients on cancer clinical trials. Treatment-related symptoms were selected from PRO-CTCAE for collection in this protocol based on the previously reported adverse event profile for sacituzumab govitecan and pembrolizumab. These symptoms are decreased appetite, nausea, vomiting, constipation, diarrhea, abdominal pain, shortness of breath, hair loss, and fatigue. PRO-CTCAE responses are scored from 0 to 4 with no standardized scoring rules.

Assessments will be conducted at the below timepoints:

- Baseline
- Every 9 weeks at the day 1 visit following restaging visits
- At the end of treatment visit

Retreatment patients will complete assessments at the below timepoint:

- Every 9 weeks at the day 1 visit following restaging visits
- At the end of treatment visit

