The assessments should be completed in clinic at study visits at the above timepoints. Quality of life assessments that are not collected at the protocol-specified collection time points will not be protocol violations. Retreatment assessments are optional.

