- m. End of treatment (EOT) visit is to occur within 45 days of final administration of study treatment, at the time of the subsequent visit that follows progression/other off treatment reason. If the EOT visit occurs within 30 days of final study treatment, an additional AE assessment is performed 30-45 days from final administration of study treatment; this may be conducted in person or by phone by the investigator or suitably trained and qualified delegate (e.g. MD, RN, NP, etc.).
- n. For those stopping treatment for reasons other than progressive disease (i.e., complete response), tumor measurements should continue to be repeated every 9-12 weeks until initiation of retreatment on this study, another anti-cancer therapy, progression, or death, whichever occurs first.
- o. Samples during follow up should be drawn every 9-12 weeks, alongside tumor assessments, for patients who come off treatment for reasons other than progressive disease until the initiation of another anti-cancer therapy, progression, or death, whichever occurs first.

- p. An adverse event assessment is performed 90 days (-15/+30 days) after the last dose of pembrolizumab (Arm A patients only). This may be conducted in person or by phone by the investigator or suitably trained and qualified delegate (e.g., MD, RN, NP, etc.).
- q. Patient reported outcomes per Section 9.9 should be performed during screening or on C1D1 prior to treatment (baseline), at the clinic visit following a restaging scan, and at end of treatment/progressive disease.
- r. For subjects on Arm A, if sacituzumab govitecan is discontinued and pembrolizumab is continued, Day 8 assessments (AE assessment, labs, vitals, etc.) are not needed.

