13 STATISTICAL CONSIDERATIONS

13.1 Study Design/Endpoints

This is a randomized phase II open label study of sacituzumab govitecan +/- pembrolizumab for patients with HR+ / HER2- MBC. Sacituzumab govitecan will be administered at a dose of 10 mg/kg IV on days 1 and 8 of each 21-day cycle, and pembrolizumab will be administered at a dose of 200 mg IV on day 1 of each 21-day cycle. The target enrollment is 110 patients; 55 per arm of treatment.

The primary endpoint is PFS defined as the time from study randomization to disease progression, per RECIST 1.1 or medical judgment, the latter based on established clinical parameters, such as rising tumor markers and physical exam evidence of progression, i.e., worsening chest wall disease, or death due to any cause, whichever occurred first. Patients alive without disease progression are censored at the date of last disease evaluation. The primary objective is to compare in the intent-to-treat (ITT) population (as defined in Section 13.5) the PFS in patients randomized to receive sacituzumab govitecan in combination with pembrolizumab (Arm A) versus those randomized to receive sacituzumab govitecan monotherapy (Arm B).

Secondary endpoints include:

- PFS according to RECIST 1.1 in the PD-L1-positive population (defined as CPS ≥ 1)
- Overall response rate (ORR) according to RECIST 1.1 in the ITT and PD-L1+ population
- Overall survival (OS) in the ITT and PD-L1+ population
- Clinical benefit rate (CBR) according to RECIST 1.1, defined as CR, PR or stable disease for ≥ 24 weeks in the ITT and PD-L1+ population
- Time to progression (TTP) in the ITT and PD-L1+ population
- Duration of response (DOR) and time to objective response (TTOR) in the ITT and PD-L1+ population
- Toxicity graded according to NCI CTCAE, Version 5.0

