13.2.1 Change in timing of the final analysis

At the time of the October 2023 DSMB reporting, it became clear that 100 PFS events would not be reached in this study (due to higher rates of treatment discontinuation for reasons other than progression than expected) and so the final PFS analysis would only occur 9 months after the last patient was randomized. This would result in a longer study timeline than expected (45 months since accrual was completed at 36 months). Changing the final analysis from 9 months after the last patient is randomized to 2 months after the last patient is randomized (i.e., 38-month study duration to primary PFS analysis) would result in approximately 5% decrease in study power. Given the treatment landscape and emerging data for TROP2 antibody drug conjugates for metastatic HR-positive/HER2-negative breast cancer, this relatively small loss of power was considered acceptable against the alternative of waiting to report the results and, hence, the final analysis will now be conducted 2 months after the last patient is randomized.

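### The patient-reported outcome plan specifies no baseline-adjusted or longitudinal analysis, although a baseline score is collected; the main cost is precision

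*Combined protocol and SAP*

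**What the plan says.** The PRO objective, in Section 1.4.4 under the correlative and exploratory objectives, is comparative: "To assess and compare the impact of treatment on Health-Related Quality of Life (HRQoL) between treatment arms".

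The analysis plan for it is one sentence in Section 13.7.4. Scale scores and global health status scores are to be "summarized and compared by treatment arm at each time point". It names no test, baseline covariate, change score, longitudinal model, analysis population or rule for missing forms. Section 9.9 and the Study Calendar add none.

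On collection, the Study Calendar (footnote q) says that PROs "should be performed during screening or on C1D1 prior to treatment (baseline), at the clinic visit following a restaging scan", and at end of treatment. Section 9.9 gives the on-treatment schedule as "Every 9 weeks at the day 1 visit following restaging visits", with a last form "At the end of treatment visit". Neither place lists a PRO during follow-up. Section 9.9 adds: "Quality of life assessments that are not collected at the protocol-specified collection time points will not be protocol violations".

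Two other statements bear on who is still completing forms. Section 13.1 says: "The target enrollment is 110 patients; 55 per arm of treatment". Section 13.2.1 says that 100 PFS events would not be reached, "due to higher rates of treatment discontinuation for reasons other than progression than expected".

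**The concern.** A comparison at each visit that ignores the baseline score leaves between-patient variation in the error term, where a covariate already on file could remove part of it. At 55 per arm, falling with each visit, that matters. Randomization is also unstratified (Section 13.3), so an unadjusted comparison carries forward part of any chance baseline imbalance.

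The second issue is selection. Forms stop at the end-of-treatment visit, so each later visit compares patients still on treatment, not the two randomized groups. If one arm stays on treatment longer, the two sets of patients may be differently selected. With separate visit-wise tables and no completion rates by arm, a reader could not tell a treatment effect on quality of life from an effect of who remained.

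The method is also left open in an open-label trial, so it could be chosen after the scores have been seen.

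**Working it through.** **The plan's own figure.** The PRO section states no power, SD or alpha. The only design figure behind the attrition calculation is the primary PFS power in Section 13.2: 80% at 100 events, hazard ratio 0.65, one-sided 0.10. By Schoenfeld's formula, z = (√100 / 2) × |ln 0.65| − 1.2816 = 2.154 − 1.282 = 0.872, so power is 80.8%. The figure reproduces, and 5.5/8.5 = 0.647 agrees with the stated hazard ratio.

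**Precision.** With the baseline score as a covariate, the variance of the arm difference at a visit is multiplied by 1 − r², where r is the correlation between baseline and visit score. The documents give no r, so a range is assumed. Power is for an assumed 0.5 SD difference, two-sided 0.05, with all 55 per arm observed.

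| r (assumed) | Variance factor | SE factor | 55 per arm acts like | Power |
|---|---|---|---|---|
| baseline not used | 1 | 1 | 55 | 74.6% |
| 0.3 | 0.91 | 0.95 | 60 | 78.5% |
| 0.5 | 0.75 | 0.87 | 73 | 85.7% |
| 0.7 | 0.51 | 0.71 | 108 | 95.7% |

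The variance reductions are therefore 9%, 25% and 51%. A simple change from baseline is not a substitute. Its variance factor is 2(1 − r), which is 1.4 at r = 0.3 (worse than ignoring baseline), 1.0 at r = 0.5 and 0.6 at r = 0.7.

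**Who is left at each visit.** The inputs are median PFS of 8.5 months (Arm A) and 5.5 months (Arm B) from Section 13.2, exponential PFS (assumed), 55 per arm, and 365.25/7/12 = 4.348 weeks per month. The progression-free share is 0.5^(months/median). At week 27, 27/4.348 = 6.21 months, giving 0.5^(6.21/8.5) = 0.603 and 0.5^(6.21/5.5) = 0.457. The SE of the unadjusted difference, in SD units, is √(1/nA + 1/nB).

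| Week | Arm A | Arm B | Patients, A v B | SE, baseline not used |
|---|---|---|---|---|
| 9 | 84.5% | 77.0% | 46.5 v 42.4 | 0.21 |
| 18 | 71.3% | 59.4% | 39.2 v 32.6 | 0.24 |
| 27 | 60.3% | 45.7% | 33.1 v 25.1 | 0.26 |
| 36 | 50.9% | 35.2% | 28.0 v 19.4 | 0.30 |
| 54 | 36.3% | 20.9% | 20.0 v 11.5 | 0.37 |

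At week 36 the SE would be 0.28, 0.26 or 0.21 with baseline as covariate, for r = 0.3, 0.5 or 0.7. The weeks are nominal, because scans, and the forms tied to them, follow treatment cycles when dosing is delayed (Section 11).

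**Size of the selection bias.** A simulation with 1,000,000 patients per arm and no true PRO effect let one latent quality-of-life trait drive the baseline score, the visit score and the time to leaving treatment. Median time on treatment was set to the design PFS medians. Assumed inputs were r = 0.5 or 0.7 and a hazard ratio for leaving of 0.82, 0.67 or 0.55 per SD of the trait. The unadjusted difference (A minus B) was −0.01 to −0.04 SD at week 9 and −0.05 to −0.12 SD at week 36. With baseline as covariate, the week 36 bias fell to between −0.01 and −0.06 SD. The largest unadjusted bias is 0.121/0.296 = 0.41 of the week 36 SE.

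**The case against.** The strongest reply is that PROs are exploratory. They sit among the correlative objectives and endpoints, outside the secondary endpoints of Section 13.1, with no hypothesis, alpha or power. A descriptive table by visit is a legitimate exploratory output and a valid description of patients while on treatment. That stands, and it is why the by-visit summaries should stay. It does not remove the gap: the stated objective is to compare arms, and other correlative endpoints in Section 13.7.1 have named tests and models.

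A reader might infer that the baseline scores are discarded. The documents do not support that. Baseline is one of the listed time points, so it will be summarized by arm, and the plan is silent on adjustment without excluding it.

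A reader might also infer that the visit-wise comparison is of different survivors and seriously biased. That is too strong. Collection ends with treatment, not death. The 60% v 46% is the progression-free share under the design alternative, not form completion, and the difference disappears if PFS does not differ. It is only a rough proxy: Section 11.1 allows treatment past first progression, Section 13.2.1 reports excess discontinuation for other reasons with no rate by arm, and a last form is due at end of treatment. The actual imbalance, and even its direction, cannot be known from the documents.

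Finally, a mixed model assumes data missing at random and estimates a different quantity from a while-on-treatment summary. That is also true, and it limits the fix.

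**Conclusion.** The concern holds, mainly as lost precision. No baseline-adjusted or longitudinal PRO analysis is specified, and using the baseline score already collected would cut the variance of the arm difference at a visit by 9% to 51% over an assumed correlation of 0.3 to 0.7.

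Selection is the lesser part. If the design medians hold, the arms may be differently selected from the first post-baseline visit. Under the assumptions tried, the bias reaches at most 0.12 SD at week 36, against an SE of about 0.30 SD. Baseline adjustment reduces that bias but does not remove it. The attrition figures rest on the plan's medians and exponential PFS; the precision and bias figures rest on assumed correlations and dropout strength.

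The point concerns the exploratory quality-of-life comparison only. Nothing here affects the primary PFS result.

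**What to change.** Keep the by-visit summaries in Section 13.7.4 and add, before scores are compared by arm:

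- For each QLQ-C30 scale and the EQ-5D score, a repeated-measures mixed model on the scheduled 9-weekly visits, with baseline score, arm, visit and arm-by-visit. Report adjusted differences with 95% confidence intervals.
- The end-of-treatment form summarized separately, because it falls at a different time for each patient and is not a common visit.
- PRO-CTCAE items analysed by an ordinal method, or a binary one for the yes/no items. Section 9.9 scores them 0 to 4 without standardized rules, so a mixed model for continuous scores does not suit them.
- Completion rates by arm and visit.
- One sensitivity analysis for informative dropout, because the model's missing-at-random assumption may fail.

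The cost is a short SAP paragraph and a little more analysis work, plus reliance on that assumption in the main model. No new data are needed, and nothing changes for patients.

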13.8 Reporting and Exclusions

13.8.1 Evaluation of Efficacy

For this Phase II trial, the efficacy evaluable population is a modified intent-to-treat (ITT) population. The modified ITT population consists of all patients who initiate protocol therapy, even if there are major protocol therapy deviations.

13.8.2 Evaluation of Safety

The safety population will be used in the safety data summaries. The safety population consists of all patients who took at least one dose of sacituzumab govitecan or pembrolizumab on study and who have at least one post-baseline safety assessment. Note that a patient who had no adverse events constitutes a safety assessment. Patients who have received at least one dose of study drug but have no post-treatment safety data of any kind will be excluded. Evaluation of safety analyses will use treatments as treated rather than as planned.

14 PUBLICATION PLAN

The results should be made public within 1 year of reaching the end of the study. The end of the study is the time point at which the last data items are to be reported, or after the outcome data are sufficiently mature for analysis, as defined in the section on Sample Size, Accrual Rate and Study Duration. If a report is planned to be published in a peer-reviewed journal, then that initial release may be an abstract that meets the requirements of the International Committee of Medical Journal Editors. A full report of the outcomes should be made public no later than three (3) years after the end of the study.

APPENDIX A PERFORMANCE STATUS CRITERIA

ECOG Performance Status Scale		Karnofsky Performance Scale	
Grade	Descriptions	Percent	Description
0	Normal activity. Fully active, able to carry on all pre-disease performance without restriction.	100	Normal, no complaints, no evidence of disease.
		90	Able to carry on normal activity; minor signs or symptoms of disease.
1	Symptoms, but ambulatory. Restricted in physically strenuous activity, but ambulatory and able to carry out work of a light or sedentary nature (e.g., light housework, office work).	80	Normal activity with effort; some signs or symptoms of disease.
		70	Cares for self, unable to carry on normal activity or to do active work.
2	In bed <50% of the time. Ambulatory and capable of all self-care, but unable to carry out any work activities. Up and about more than 50% of waking hours.	60	Requires occasional assistance but is able to care for most of his/her needs.
		50	Requires considerable assistance and frequent medical care.
3	In bed >50% of the time. Capable of only limited self-care, confined to bed or chair more than 50% of waking hours.	40	Disabled, requires special care and assistance.
		30	Severely disabled, hospitalization indicated. Death not imminent.
4	100% bedridden. Completely disabled. Cannot carry on any self-care. Totally confined to bed or chair.	20	Very sick, hospitalization indicated. Death not imminent.
		10	Moribund, fatal processes progressing rapidly.
5	Dead.	0	Dead.

APPENDIX B CONTRACEPTIVE GUIDANCE AND PREGNANCY TESTING

Woman of Childbearing Potential (WOCBP)

A woman is considered fertile following menarche and until becoming post-menopausal unless permanently sterile (see below)

Women in the following categories are not considered WOCBP:

- Premenarchal
- Premenopausal female with 1 of the following:
 - Documented hysterectomy
 - Documented bilateral salpingectomy
 - Documented bilateral oophorectomy
- Note: Documentation can come from the site personnel's review of the participant's medical records, medical examination, or medical history interview.
- Postmenopausal female
 - A postmenopausal state is defined as no menses for 12 months without an alternative medical cause.
 - A high follicle stimulating hormone (FSH) level in the postmenopausal range may be used to confirm a postmenopausal state in women not using hormonal contraception or hormonal replacement therapy (HRT). However, in the absence of 12 months of amenorrhea, confirmation with two FSH measurements in the postmenopausal range is required.
 - Females on HRT and whose menopausal status is in doubt will be required to use one of the non-hormonal, highly effective, contraception methods if they wish to continue their HRT during the study. Otherwise, they must discontinue HRT to allow confirmation of postmenopausal status before study enrollment.

Contraception Requirements

Male Participants:

Male participants with female partners of childbearing potential are eligible to participate if they agree to one of the following for the duration of study treatment and 3 months after the last dose of study treatment:

- Be abstinent from penile-vaginal intercourse as their usual and preferred lifestyle (abstinent on a long term and persistent basis) and agree to remain abstinent
- Use a male condom plus partner use of a contraceptive method with a failure rate of <1% per year as described in Table 9 when having penile-vaginal intercourse with a woman of childbearing potential who is not currently pregnant.
 - Note: Men with a pregnant or breastfeeding partner must agree to remain abstinent from penile-vaginal intercourse or use a male condom during each episode of penile penetration.

Female Participants:

Female participants of childbearing potential are eligible to participate if they agree to use a highly effective method of contraception consistently and correctly as described in Table 1 starting with the first dose of study medication through 180 days (6 months) after the last dose of study medication.

Table 1 Highly Effective Contraception Methods

Highly Effective Methods That Have Low User Dependency Failure rate of <1% per year when used consistently and correctly.

• Intrauterine device (IUD)• Bilateral tubal occlusion

• Vasectomized partner A vasectomized partner is a highly effective contraception method provided that the partner is the sole male sexual partner of the WOCBP and the absence of sperm has been confirmed. If not, an additional highly effective method of contraception should be used.

• Sexual abstinence Sexual abstinence is considered a highly effective method only if defined as refraining from heterosexual intercourse during the entire period of risk associated with the study treatment. The reliability of sexual abstinence needs to be evaluated in relation to the duration of the study and the preferred and usual lifestyle of the participant.)

Notes: Use should be consistent with local regulations regarding the use of contraceptive methods for participants of clinical studies.

Pregnancy Testing

WOCBP should only be included after a negative highly sensitive urine or serum pregnancy test.

Following initiation of treatment, pregnancy testing will be performed whenever an expected menstrual cycle is missed or when pregnancy is otherwise suspected; at the time points specified in the Schedule of Activities, and as required locally.

